#### LIST OF ABBREVIATIONS AND RELEVANT DEFINITIONS

ABR General Assessment and Registration form (ABR form), the application

form that is required for submission to the accredited Ethics Committee;

in Dutch: Algemeen Beoordelings- en Registratieformulier (ABR-

formulier)

AE Adverse Event

AR Adverse Reaction

**CA** Competent Authority

**CCMO** Central Committee on Research Involving Human Subjects; in Dutch:

**Centrale Commissie Mensgebonden Onderzoek** 

CV Curriculum Vitae

**DSMB** Data Safety Monitoring Board

**EU** European Union

**EudraCT** European drug regulatory affairs Clinical Trials

**GCP** Good Clinical Practice

GDPR General Data Protection Regulation; in Dutch: Algemene Verordening

Gegevensbescherming (AVG)

IB Investigator's Brochure

IC Informed Consent

IMP Investigational Medicinal Product

IMPD Investigational Medicinal Product Dossier

METC Medical research ethics committee (MREC); in Dutch: medisch-ethische

toetsingscommissie (METC)

(S)AE (Serious) Adverse Event

SPC Summary of Product Characteristics; in Dutch: officiële

productinformatie IB1-tekst

Sponsor The sponsor is the party that commissions the organisation or

performance of the research, for example a pharmaceutical

company, academic hospital, scientific organisation or investigator. A party that provides funding for a study but does not commission it is not

regarded as the sponsor, but referred to as a subsidising party.

SUSAR Suspected Unexpected Serious Adverse Reaction

**UAVG** Dutch Act on Implementation of the General Data Protection Regulation;

in Dutch: Uitvoeringswet AVG

WMO Medical Research Involving Human Subjects Act; in Dutch: Wet Medisch-

wetenschappelijk Onderzoek met Mensen

## aSBO Adhesive Small Bowel Obstruction

#### **SUMMARY**

Rationale: Adhesive small bowel obstruction (aSBO) is a frequent surgical emergency, associated with 3-8% hospital mortality and a high risk of recurrence (20% at two years of follow-up). ASBO can be treated conservatively or by emergency surgery. In the absence of bowel ischemia or strangulation, conservative treatment is often preferred, to avoid the excess morbidity and mortality from emergency surgery. Recent epidemiological studies, however, demonstrate a considerable higher recurrence risk of aSBO after conservative treatment that is associated with hospital readmissions and lower survival. Elective adhesiolysis following successful conservative treatment might reduce these long-term risks whilst avoiding the high complication rate of emergency surgery.

**Objective**: We aim to investigate the efficacy of elective adhesiolysis following conservative treatment for aSBO as compared to the current state of the art (wait-and-see policy) to prevent long-term recurrence of aSBO. Further we will evaluate quality of life, healthcare and societal costs.

**Study design:** Multicenter open-label randomized controlled trial, including 380 patients. **Study population:** Adult patients who recovered from aSBO by conservative treatment. Patients that are inoperable for medical, anaesthesiological or surgical reasons are excluded. **Intervention (if applicable)**: The intervention of investigation is elective adhesiolysis. Adhesiolysis is an abdominal procedure in which all adhesions are cut, and adhesion prevention applied to reduce the risk of adhesion reformation. The intervention is compared to wait-and-see policy (the current standard treatment)

**Main study parameters/endpoints:** Primary outcome is recurrence, defined as readmission for obstructive systems with aetiology of adhesions confirmed by CT. We hypothesize a 50% reduction in recurrence in the intervention arm. Secondary outcomes are morbidity from surgery, health-related quality of life (EQ5D), healthcare costs and societal costs (iMCQ and iPCQ)

Nature and extent of the burden and risks associated with participation, benefit and group relatedness:

Patients in the intervention group are exposed to abdominal surgery, which is associated with a moderate risk of minor complications such as wound infection and haemorrhage, and small risk of severe complications such as iatrogenic bowel injury. According to our hypothesis, a potential benefit is the reduction in the risk of recurrences. Recurrence of aSBO is associated with a risk of readmissions, reinterventions, and also increased long-term mortality.

#### 1. INTRODUCTION AND RATIONALE

Adhesive small bowel obstruction (aSBO) is a frequent abdominal surgical emergency causing an estimate of 4,000 hospital admission in the Netherlands and Belgium annually.(1, 2) ASBO is associated with significant morbidity and mortality, in particular when emergency surgery is needed to resolve the obstruction. In a recent Dutch snapshot study in which 34 hospitals participated, mortality after operative treatment was 4.2%.(1) In the NELA report from the U.K., ASBO was the most frequent cause of overall death in emergency abdominal surgery, and the 30-day mortality rate of surgery for aSBO was 7%.(3) In comparison, mortality from conservative treatment consisting of gastric decompression, nill per os, and iv fluids, was only 1.6% in the Dutch snapshot study.(1) The burden of aSBO for society is also huge, although there is relative little specific data on the societal costs and QoL after aSBO. Direct hospital costs for an episode of ASBO are calculated at  $\leq 2,277 \pm 265$  for conservative treated episodes, and  $\leq 16,305 \pm 2,513$  for operatively treated episodes.(4) The majority of patients with aSBO are in working age. In our experience, most patients have an extended sick leave of several weeks after an episode of aSBO, and some may never return to work at all. In a Scandinavian study the prevalence of chronic abdominal pain after an episode of aSBO was 20%.(5)

Because of the increased morbidity and mortality of emergency surgery, an international clinical practice guideline advises a trial of conservative treatment in the absence of signs of acute bowel ischemia or strangulation.(2) Nevertheless, the preference for conservative treatment is increasingly subject to debate. There is a recent body of evidence showing that the risk of longterm recurrence is considerable higher after conservative treatment. In a population study, 2year recurrence after conservative treatment was estimated at approximately 20%, as compared to 13% after emergency surgery for patients admitted for their first episode of aSBO.(6, 7) The risk of recurrence increases with longer follow-up, and recurrence risks up to 40% have been reported at 10 years of follow-up after an initial episode of aSBO.(8, 9) Recurrence risks of aSBO is even higher in patients with more than one episode in history (30-60%).(10) At long-term follow-up operative treatment is associated with lower risks of recurrence and a subsequent lower risk of mortality (hazard ratio, 0.80; 95% confidence interval, 0.75-0.86).(6) A RCT with 4 years of follow-up demonstrated that the risk of recurrence following operative treatment can further be reduced from 11% to 2.2% when using adhesion barriers.(11) For these reasons, part of the hospitals in the Netherlands and Belgium already treat aSBO more frequently by surgery. Currently, a conservative wait-and-see policy is the standard treatment applied after primary admission with an aSBO. Elective adhesioslysis is already being applied selectively in clinical practice, especially in patients with a recurrent aSBO.

Another alternative strategy might involve elective adhesiolysis after the resolution of aSBO with conservative treatment. Elective adhesiolysis is a reimbursed procedure in the Netherlands and Belgium, primarily performed in expert centers for patients with chronic abdominal complaints after surgery. In selected patients, along with the use of adhesion barriers to reduce the risk of adhesion regrowth, this procedure results in long-term control of chronic symptoms. (12, 13) A recent study from our group suggests that this procedure also effectively reduces the risk of (recurrent) aSBO with more than 65%, while avoiding the morbidity from emergency

Version number: 2, 25-04-2025

10 of

surgery.(14) In this study 122 patients with chronic complaints from adhesions were included, of whom 60 had previous episodes of aSBO. In both the entire cohort and the subgroup of patients with previous aSBO, elective adhesiolysis resulted in a significant 3-fold reduction in incidence of aSBO during 5-year follow-up.

The aim of the present study is to assess the efficacy and safety of elective adhesiolysis to reduce long-term recurrence of aSBO, as compared to a wait-and-see policy. Primary outcome is the 2-year risk of readmission for recurrence, secondary outcomes are chronic abdominal complaints, mortality, operative morbidity, quality of life, and healthcare and societal costs (measured by iMCQ and iPCQ). In the selection of outcomes we made sure to incorporate the outcomes from the ASBO core outcome set that a relevant for long-term evaluation.(15)

## 2. OBJECTIVES

## **Primary Objective:**

To assess the efficacy and safety of elective adhesiolysis with application of adhesion barrier to prevent recurrence of aSBO as compared to wait-and-see.

Recurrence is defined as a hospital readmission for symptoms of bowel obstruction, after exclusion of other causes of bowel obstruction by CT (see outcomes).

## Secondary Objective(s):

To assess impact of elective adhesiolysis as compared to wait-and-see on health economics (in accordance to the Dutch and Belgian standards), Quality of Life, chronic abdominal complaints, costs, as well as the cost-effectiveness from a healthcare and societal perspective..

## 3. STUDY DESIGN

This is a multicenter randomized open-label controlled trial including 380 patients. The setting of the trial is hospital care. The trial will be performed as an open label trial, because of the invasiveness of the intervention that cannot be blinded for. The control group will have a wait-and-see policy which is in accordance to the current state-of-the-art. Follow-up for the primary outcome will be 2 years. In addition a longer-term follow-up of 5 years will be performed using record linking. Cross-over from the control to the intervention group after development of a recurrence are allowed, as we expect some patients might develop a preference not to await further recurrences. The main criterium that has to be met for cross-over from the control group to the intervention group is the recurrence of an aSBO in a control patient. Cross-over will not impact the primary outcome, but may impact some of the secondary outcomes. Cross-overs will be analyzed according to intention to treat.

#### 4. STUDY POPULATION

## 4.1 Population (base)

#### 4.2 Inclusion criteria

In order to be eligible to participate in this study, a subject must meet all of the following criteria:

- Adult patients aged 18 years and older who have recently recovered from aSBO by small bowel obstruction managed by conservative treatment.
- ASBO is defined as an acute episode of bowel obstruction, causing symptoms of bloating, nausea and abdominal pain, and requiring hospital admission.

  In addition, the following criteria have to be met:
  - Patients who have previously been operated (high a prior risk of adhesions)
    are required to have no signs of other causes of bowel obstruction on imaging
    studies (CT- scan).
  - Patients with no previous operation in history (low a prior risk of adhesions) are required to have typical signs for aSBO on imaging studies (abrupt change of bowel calibre, closed loop, or signs of torsion on vessels in the mesentery on CT-scan).

#### 4.3 Exclusion criteria

A potential subject who meets any of the following criteria will be excluded from participation in this study:

- Patient who are unfit for operation for surgical, anesthesiological or medical reasons as determined by multidisciplinary team assessment or pre-operative screening
- Patients with active malignancy, reducing life expectancy
- Patient who has undergone surgery for previous episodes of aSBO in the past six months.
- Patient who has undergone previous complete adhesiolysis with use of adhesion barriers.
- Pregnancy

#### 4.4 Sample size calculation

Primary outcome is the time to recurrence measured at two years of prospective follow-up. We will perform a superiority trial. Based on previous literature, we expect 20% recurrence in 2-year with wait-and-see policy (based on a mix of patients with a first and recurrent episode of aSBO) and a 10% recurrence rate after intervention, resulting in a hazard ratio (HR) of approximately 0.47.

We estimated that if 378 patients were randomly assigned in a 1:1 ratio (i.e., 189 per group) to the intervention group or the control group, our study would have 80% power to detect an HR for recurrence of adhesive small bowel obstruction of approximately 0.47 at a two-sided  $\alpha$  level of 0.05. After rounding the total number of patients up, we aim to include a total of 380 patients. Analysis will be performed by intention to treat basis, using survival analysis. We will use cox regression to be able to apply multivariable analysis to account for covariates such as previous episodes of ASBO.

## 5. TREATMENT OF SUBJECTS

#### 5.1 Investigational treatment

Elective adhesiolysis will be compared to a wait-and-see policy. Elective adhesioslysis is selectively applied in clinical practice, especially in patients with a recurrent aSBO. Elective adhesiolysis is a surgical procedure in which all adhesions in the abdomen are released. Elective adhesiolysis is preferably performed laparoscopy, but the precise surgical approach is adjusted to the expected location and extent of the adhesions, presence of a stoma, abdominal wall defects, as well as the surgical history and locations of previous scarring. We expect an open approach or conversion from laparoscopy to open surgery to be required in 10-15% of patients. The typical duration of hospital admission is 1-2 days for laparoscopic adhesiolysis and 5-7 days for open or converted adhesiolysis. Patients typically have one control visit to the outpatient clinical between 2-4 weeks after discharge to assess surgical healing.

In accordance to the surgical protocols of expertise centres for adhesiolysis and the advice of the international clinical practice guideline for aSBO, adhesion barriers are used as part of the standard of care during elective adhesiolysis, to reduce the risk of regrowth of adhesion after their release.(2) The adhesion barriers are registered and authorized medical devices. They will only be used in accordance to their registered and intended use. The application of adhesion barriers is an easy and low-tech intervention that requires no specific surgical skill or learning curve. Information session will be held in all participating centres prior to start of the trial.

The adhesion barrier to be used in laparoscopic adhesiolysis is Icodextrin 4% (Adepttm). This barrier has previously been found to be safe and effective in reducing adhesion formation in abdominal surgery.(16) Specifically, it has demonstrated to reduce the risk of readmission for aSBO when applied during emergency surgery for aSBO.(11) The barrier was also used in a recent cohort, demonstrating reduced incidence of aSBO after elective adhesiolysis.(14)

The barrier to be used in open or converted surgery is hyaluronate carboxymethylcellulose (Seprafilmtm). This barrier has also been found safe and effective in reducing adhesion formation in abdominal surgery. In a meta-analysis the barrier was effective is reducing the risk of future reoperation for aSBO when applied in colorectal surgery.(16)

Despite the existing evidence for the efficacy of adhesion barriers, they have only partly been implemented in hospitals in the Netherland and Belgium. In our group, there was

broad consensus based on the available data that adhesion barriers should be used as part of a good elective adhesiolysis. This consensus was also supported by the surgeons from the participating centres in the Netherlands and Belgium that at present do not use adhesion barriers in their daily routine. Therefore we decided to standardize their use in the trial. Barriers are provided as part of the trial to minimize the risk of difficulties with inclusion, or significant delays in local approval of a lack of availability of adhesion barriers. The use of barriers will be a focus in the implementation plan that will be made by the end of the trial.

No specific intervention or follow-up is performed in the control group of wait-and-see policy. Current standard treatment for patients with a primary aSBO is the wait-and-see policy.

#### 6. METHODS

## 6.1 Study parameters/endpoints

## 6.1.1 Main study parameter/endpoint

The primary outcome of the study is recurrence at 2-years of follow-up.

Recurrence is defined as a readmission for symptoms of small bowel obstruction, including lower abdominal pain, bloating and nausea with or without vomiting. In addition imaging by CT-scan should not show indications of other causes of bowel obstruction (such as an incarcerated abdominal wall hernia or tumour), which is over 90% accurate for the diagnosis of ASBO.

The incidence of recurrent ASBO increases over time. We deliberately preferred a 2-year follow-up as the primary outcome, because at this time frame it is feasible to prospectively follow-up on patients with low loss of data, and also ethically to avoid long delays in implementation of results.

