#### Recurrence

Patients will present at their local hospital (referral of operative centre) in case of symptoms of recurrence of bowel obstruction, including lower abdominal pain, bloating, nausea, and vomiting. Although most cases of bowel obstruction are caused by adhesions, especially after previous episodes of aSBO, there are a few other aetiologies of bowel obstruction such as strangulated abdominal wall hernia or tumours. To confirm the adhesive aetiology of small bowel obstruction a CT-scan will be made. CT-scan is known to be more than 90% accurate in distinguishing adhesions from alternative causes of bowel obstruction.(2) A readmission for obstructive symptom with CT or operative confirmation of adhesive aetiology will be scored as recurrence under the primary outcome.

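### The primary event, recurrence of aSBO, is defined differently across the protocol, so the same readmission can be an event under one section and not under another

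*Protocol*

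**What the plan says.** The Protocol states what counts as a recurrence in five places.

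- **Summary.** The outcome is "defined as readmission for obstructive systems with aetiology of adhesions confirmed by CT". This asks for positive confirmation and names no operative route.
- **Section 2, Primary Objective.** A readmission for obstructive symptoms counts "after exclusion of other causes of bowel obstruction by CT". This works by exclusion and names no operative route.
- **Section 6.1.1.** "Recurrence is defined as a readmission for symptoms of small bowel obstruction, including lower abdominal pain, bloating and nausea with or without vomiting". The only imaging condition follows: "In addition imaging by CT-scan should not show indications of other causes of bowel obstruction". This is again exclusion by CT only.
- **Section 6.3, Recurrence.** "A readmission for obstructive symptom with CT or operative confirmation of adhesive aetiology will be scored as recurrence under the primary outcome". This asks for positive confirmation, by either route. The same paragraph plans a CT when a patient presents.
- **Section 6.3, Cross-over of patients.** A control may cross over after a new episode of acute obstruction that needs admission, with no other cause on CT. The paragraph refers back to section 4.1 for the definition, although the criteria are listed in 4.2.

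Section 3 makes a control's recurrence the main criterion for cross-over and adds: "Cross-over will not impact the primary outcome, but may impact some of the secondary outcomes". Section 6.2 states that subjects, surgeons and researchers are not blinded. Section 4.4 plans for 20% against 10% recurrence at two years, a hazard ratio of about 0.47, and 378 patients for 80% power, rounded up to 380.

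**The concern.** The definitions differ in substance. Two of them (Summary; 6.3 Recurrence) need evidence for adhesions. The other two that define the endpoint (2; 6.1.1) need only the absence of evidence for something else. Read literally, section 6.1.1 does not require obstruction to be shown at all. Its symptoms (abdominal pain, bloating, nausea) overlap with the chronic complaints that section 6.1.2 collects separately and that section 9.4 describes as common after aSBO. Some readmissions for these symptoms may therefore have a CT without obstruction.

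Centres classify events from the protocol. If they apply different sections, the primary outcome is not the same quantity across centres. Section 6.3 also provides for checking possible missed episodes against medical records, but does not say which definition they are checked against. With few events planned, a handful of ambiguous cases matters. Because the trial is unblinded, an ambiguous rule also leaves more room for judgement made with knowledge of the arm.

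**Working it through.** **1. The definitions applied to three kinds of case**

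| Case | Summary | Section 2 | 6.1.1 | 6.3 Recurrence | 6.3 Cross-over |
|---|---|---|---|---|---|
| CT shows obstruction, no other cause | yes* | yes | yes | yes* | yes |
| Symptoms; CT shows neither obstruction nor another cause | no | yes (literal) | yes (literal) | no | unclear: acute obstruction is required, but the CT test is exclusion only |
| Adhesive obstruction proven at operation, no CT | no | no route | no route | yes | not met as worded |

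*If absence of another cause is taken as confirming adhesions.

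The first row is the common case, and the sections agree. The second and third rows change status with the section used.

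**2. The plan's own figures**

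Inputs from section 4.4: 20% and 10% at two years, 189 per arm, two-sided alpha 0.05.

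- HR = ln(0.90)/ln(0.80) = 0.472.
- Schoenfeld events for 80% power = 4(1.960 + 0.842)²/(ln HR)², rounded up to 56. Dividing by the mean event probability of 0.15 gives 374 patients, close to the stated 378.
- Expected events = 189 × (0.20 + 0.10) = 56.7.
- Power = Φ(½ × √56.7 × |ln 0.472| − 1.960) = 80.7% (81.1% with HR 0.47).

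The stated sample size reproduces. There is no arithmetic error in it.

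**3. Illustration: symptom-only events in both arms**

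The protocol gives no rate, so q below is assumed. It is the share of otherwise event-free patients who gain a symptom-only event. Then p(control) = 0.20 + 0.80q, p(intervention) = 0.10 + 0.90q, and added events = 189 × (0.80 + 0.90) × q. HR and power follow as in step 2.

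| q | Control | Intervention | Added events | Total events | HR | Power |
|---|---|---|---|---|---|---|
| 0 | 20.0% | 10.0% | 0 | 56.7 | 0.472 | 80.7% |
| 2% | 21.6% | 11.8% | 6.4 | 63.1 | 0.516 | 74.8% |
| 3% | 22.4% | 12.7% | 9.6 | 66.3 | 0.536 | 72.0% |
| 5% | 24.0% | 14.5% | 16.1 | 72.8 | 0.571 | 66.7% |

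**4. Illustration: the same rates in controls only, no true effect**

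Both arms have a true rate of 20%, and only controls gain events. Control rates become 21.6/22.4/24.0% against 20%. The chance of a significant result favouring surgery is 5.8/8.3/15.5%, against a nominal 2.5%. This shows sensitivity and is not a prediction.

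**5. Illustration in the other direction: events lost**

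If 5/10/20% of true recurrences went uncounted in both arms, the HR would stay near 0.47 to 0.48 but power would fall to 78.3/75.7/70.0%. A definition that is too strict therefore also costs power.

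**The case against.** The strongest reply is that the intent is clear and only the wording is loose. Section 6.1.1 speaks of other causes of obstruction, which presupposes an obstruction, and it cites the accuracy of CT for diagnosing aSBO. The sentence in 6.3 that says what will be scored under the primary outcome requires confirmation, plans a CT and accepts operative proof. This is a fair account of what the authors probably meant. It does not remove the conflict, because 6.1.1 is the formal endpoint section and does not state the requirement. It does limit what can be inferred:

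- A reader might infer that the protocol deliberately counts an unremarkable CT as a recurrence. That follows only from the literal wording of sections 2 and 6.1.1.
- A reader might infer that the most severe recurrences will be missed. Since 6.3 plans a CT and accepts operative findings, the gap for cases operated on without CT is probably small.
- A reader might infer a bias in favour of surgery, because a recurrence opens cross-over for controls. The cross-over paragraph asks for a new acute obstruction, which is stricter than 6.1.1 read literally, and the decision is shared with the surgeon. Unblinded labelling could also vary in the intervention arm. Neither the direction nor the size of a bias is established.
- A reader might infer that the section 3 statement on cross-over is wrong. As to timing it is right: cross-over follows the first recurrence, so time to first event is already fixed. It does not address the separate possibility that access to cross-over influences how an event is labelled.

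The power figures also assume that the 20% and 10% taken from the literature contain no symptom-only readmissions. The document does not allow that to be checked.

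**Conclusion.** The inconsistency is real and concerns the primary outcome. Sections 2 and 6.1.1 use exclusion on CT, the Summary requires confirmation by CT, the Recurrence paragraph of 6.3 accepts CT or operation, and the cross-over paragraph adds another wording. At least two kinds of case are events under some sections and not under others. This conclusion rests on the text alone and needs no assumed rate.

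The size of the effect is unknown. If symptom-only events occurred in 2 to 5% of event-free patients in both arms, power would fall from about 81% to between 75% and 67%. If they occurred at those rates in controls only, the chance of a false benefit would be about 6 to 16% instead of 2.5%. Both ranges depend on rates that the protocol does not supply, and the second also depends on a direction that nothing in the document establishes. They show that a trial with about 57 planned events is sensitive to the event rule, not that its result will be biased.

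**What to change.** Use one event definition, word for word, in the Summary, section 2, section 6.1.1 and both paragraphs of section 6.3 (Recurrence and Cross-over). For the endpoint it should state that:

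- the patient is readmitted and small bowel obstruction is present on CT or at operation, with no other cause found;
- operative findings suffice when no CT was made;
- cases with neither CT nor operation are scored by a stated rule.

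The CT signs listed in section 4.2 should not be required for every event. Section 4.2 asks for them only in patients without previous surgery, so a recurrence would otherwise be held to a stricter standard than the index episode of a previously operated patient.

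Report readmissions for symptoms without obstruction on CT as a separate outcome, and run the literal 6.1.1 wording as a sensitivity analysis. Classifying events from reports with the allocation removed would answer the open-label question and is optional. The cross-over wording has to be reconciled with the endpoint. If the sponsor wants a different trigger on clinical grounds, the protocol should say that the two differ on purpose.

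The cost is protocol and case report form wording. The downside is a possibly slightly lower event count if symptom-only readmissions were expected to count.
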